5.4.1.3 Other reasons for cetuximab discontinuation

If a subject develops an intercurrent illness (i.e., infection) that, in the opinion of the investigator mandates interruption of cetuximab therapy, that intercurrent illness must resolve within a time frame such that no more than two consecutive infusions are withheld. After the interruption of treatment, the subject will continue with a cetuximab dose of 250 mg/m² at subsequent visits or the last dose before the interruption if there have been previous dose reductions.

If therapy must be withheld for a longer period of time, the subject will be removed from the study treatment. In special cases, the investigator may request that the patient continues to receive cetuximab (the investigator must ask permission from the Investigator-Sponsor).

5.4.2 5-Fluorouracil

Toxicities solely related to chemotherapy do not lead to a dose modification or interruption of cetuximab and vice versa.

5.4.2.1 Dose modifications and treatment alterations for 5-FU

The dose of 5-FU will be modified, if the following toxicities (Table 3) are observed during the radiochemotherapy on the planned day of 5-FU infusion.

Once a 5-FU dose modification has occurred, the dosage may not be re-escalated for this patient. If therapy is delayed for longer than 2 weeks, the patient will be withdrawn from the study.

If on the day of planned 5-FU infusion one of the following toxicities occurs, a dose modification according to the following scheme will be performed:

Table 3: Dose modification for 5-FU in case of toxicities on the day of planned 5-FU infusion

Toxicity	CTC - Grade	Continue with Chemotherapy	Dose modification
Neutropenia	ANC $\geq 1.5 \times 10^9/L$	Yes	No
	ANC $< 1.5 \times 10^9/L$	Delay until ANC $\geq 1.5 \times 10^9/L$	No
	ANC $< 0.5 \times 10^9/L$	Delay until ANC $\geq 1.5 \times 10^9/L$	Yes 5-FU 75% of original dose
Thrombocytopenia	Platelets $\geq 100 \times 10^9/L$	Yes	No
	Platelets $< 100 \times 10^9/L$	Delay until platelets $\geq 100 \times 10^9/L$	No
	Platelets $< 25 \times 10^9/L$	Delay until platelets $\geq 100 \times 10^9/L$	Yes 5-FU 75% of original dose
Diarrhea	Grade 0-1	Yes	No
	Grade 2	Delay until resolved to grade < 2	No
	Grade 3	Delay until resolved to grade < 2	1 st occurrence: No 2 nd occurrence: Yes 5-FU 75% of original dose
	Grade 4	withdrawal	withdrawal
Mucositis/Stomatitis	Grade ≥ 1	Delay until resolved	Yes 5-FU 75% of original dose
Skin (except irradiated region and cetuximab-related skin toxicities)	Grade ≥ 2	Delay until grade 0-1	Yes 5-FU 75% of original dose
Further non-hematological toxicities (except nausea/vomiting and alopecia)	Grade 0-1	Yes	No
	Grade 2-3	Delay until grade 0-1	Yes 5-FU 75% of original dose
	Grade 4	withdrawal	withdrawal

If at any time during the radiochemotherapy one of the following toxicities occurs, a dose modification of 5-FU at the next planned infusion will be performed according to the following scheme:

Table 4: Dose modification for 5-FU in case of toxicities during radiochemotherapy

Toxicity	CTC-Grade	Dose modification
Neutropenia	ANC < 0.5 x 10 ⁹ /L	5-FU 75% of original dose
Thrombocytopenia	Platelets < 50 x10 ⁹ /l	5-FU 75% of original dose
Diarrhea	≥ Grad 3 (≥ stools/day or incontinence)	5-FU 75% of original dose
Nausea/vomiting	≥ Grad 3	5-FU 75% of original dose

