4.2.4 Removal of patients from the study or study treatment

Patients are free to discontinue the study at any time without giving their reason(s).

The patient must be withdrawn from study treatment in the event of any of the following:

- Withdrawal of the patient's consent
- Occurrence of an exclusion criterion which is clinically relevant and affects the patient's safety
- Occurrence of AEs, if discontinuation is desired or considered necessary by the patient and/or investigator
- Occurrence of pregnancy during treatment
- Lack of subject compliance
- A delay of treatment with cetuximab for more than 2 consecutive weeks
- Occurrence of any grade 4 toxicities related to cetuximab
- Occurrence of \geq grade 3 allergic/hypersensitivity reaction related to cetuximab
- Occurrence of disease progression

If there is a medical reason for withdrawal, the patient will remain under the supervision of the investigator until the AEs have been resolved or declined to baseline values.

If a patient has failed to attend scheduled assessments in the study, the investigator must determine the reasons and circumstances as completely and accurately as possible.

In case of premature discontinuation of the study treatment by a patient, the investigations scheduled for the last visit should be performed, if possible. In any case, the CRF section entitled "End of Treatment" must be completed.

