5.4.1.1 Skin toxicities

If a subject experiences a grade 3 skin toxicity (as defined in the US National Cancer Institute's - Common Toxicity Criteria [NCI-CTC], Version 4.0), cetuximab therapy may be delayed for up to two consecutive infusions without changing the dose level. For grade 1 or 2 acne-like rash treatment with topical antibiotics (e.g. benzoylperoxide, erythromycin) or systemic antibiotics (e.g. oral tetracyclines such as doxycycline 100 mg od) should be considered. Patients with grade ≥ 3 reactions should be referred to the dermatologist for advice and management. If pruritus occurs an oral antihistamine is advised. In case of dry skin the use of emollient creams is beneficial. Fissures may occur in dry skin and topical dressings are helpful. If the toxicity resolves to grade 2 or less by the following treatment period, treatment may resume. With the second and third occurrences of grade 3 skin toxicity, cetuximab therapy may again be delayed for up to two consecutive weeks with concomitant dose reductions to 200 mg/m² and 150 mg/m², respectively. Cetuximab dose reductions are permanent. Subjects should discontinue cetuximab if more than two consecutive infusions are withheld or a fourth occurrence of a grade 3 skin toxicity occurs despite appropriate dose reduction (see figure 1).

However, if in the opinion of the investigator the discontinuation of cetuximab is considered necessary, the subject should be withdrawn immediately.

The dose of cetuximab will be adjusted for cetuximab-related grade 3 skin toxicities only. Cetuximab therapy will not be withheld for chemotherapy related toxicities. Therefore, in the event that the next infusion of chemotherapy is delayed, the subject will receive cetuximab as previously planned.

Figure 1: Treatment adjustment in the event of grade 3 skin toxicity considered to be related to cetuximab.

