5.4.1.2 Allergic/hypersensitivity reactions

In each case of allergic/hypersensitivity reaction, the investigator should implement treatment measures according to the best available medical practice. Based on previous experience with cetuximab allergic/hypersensitivity reactions, the treatment guidelines as described in Table 2 may be applicable.

Table 2 Treatment adjustment in the event of cetuximab caused allergic / hypersensitivity reaction.

CTC Grade Allergic/ Hypersensitivity Reaction	Treatment
Grade 1	Decrease the cetuximab infusion rate by 50% and monitor closely for any worsening. The total infusion time for cetuximab should not exceed 4 hours.
Grade 2	Stop cetuximab infusion. Administer bronchodilators, oxygen, etc. as medically indicated. Resume infusion at 50% of previous rate once allergic/hypersensitivity reaction has resolved or decreased to Grade 1 in severity, and monitor closely for any worsening
Grade 3 or Grade 4	Stop the cetuximab infusion immediately and disconnect infusion tubing from the subject. Administer epinephrine, broncho- dilators, antihistamines, glucocorticoids, intravenous fluids, vasopressor agents, oxygen, etc., as medically indicated. Subjects must be withdrawn immediately from the

	treatment and must not receive any further cetuximab treatment.
--	--

Re-treatment following allergic/hypersensitivity reactions:

Once a cetuximab infusion rate has been decreased due to an allergic/hypersensitivity reaction, it will remain decreased for all subsequent infusions. If the subject has a second allergic/hypersensitivity reaction with the slower infusion rate, the infusion should be stopped and the subject should be removed from the study. If a subject experiences a Grade 3 or 4-allergic/hypersensitivity reactions at any time, cetuximab should be discontinued.

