5.4.3 Cisplatin

5.4.3.1 Dose modifications and treatment alterations for cisplatin

Table 5: Dose modification regarding the cisplatin induced renal toxicity prior to every new course:

Creatinine value	Dose modification
≤ 1.5 mg/dl	no dose modification
> 1.5 mg/dl	Delay until creatinine is < 1.5 mg/dl, then restart with 50% of original dose

Additionally the following criteria have to be fulfilled prior to every chemotherapy course:

- Neutrophils ≥ 1,5 x 10⁹/L
- Thrombocytes ≥ 100 x 10⁹/L
- Diarrhea NCI-CTC Version 4.0 Grade < 2

If these parameters are not appropriately at the scheduled time point of the new course, cisplatin administration has to be discontinued until the criteria above will be fulfilled.

If cisplatin cannot be administered for less than two weeks, the therapy will be continued with the initial dosing.

If cisplatin cannot be administered for more than two weeks the administered dose will be 75% of the original value.

If at any time during the radiochemotherapy one of the following toxicities occurs, a dose modification of cisplatin at the next planned infusion will be performed according to the following scheme:

Table 6: Dose modification for cisplatin in case of toxicities during radiochemotherapy

Toxicity	CTC-Grade	Dose modification
Neutropenia	ANC < 0.5 x 10 ⁹ /L	Cisplatin 75% of original dose
Thrombocytopenia	Platelets < 25 x10 ⁹ /l	Cisplatin 75% of original dose
Further non-hematological toxicities (except nausea and vomiting)	Grade 3	Cisplatin 75% of original dose
	Grade 4	Discontinuation of chemotherapy

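### After a chemotherapy delay of more than two weeks the 5-FU rule takes the patient off study while the cisplatin rule restarts at 75%, and continued survival follow-up is only implied

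*Combined protocol and SAP*

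**What the plan says.** **5-FU (5.4.2.1).** Table 3 delays 5-FU for, among other things, neutrophils below 1.5 x 10⁹/L, platelets below 100 x 10⁹/L and diarrhoea of grade 2 or 3. The text above the table adds: "If therapy is delayed for longer than 2 weeks, the patient will be withdrawn from the study".

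**Cisplatin (5.4.3.1).** The same three limits must be met before each course. If they are not, "cisplatin administration has to be discontinued until the criteria above will be fulfilled". For a long delay the rule is: "If cisplatin cannot be administered for more than two weeks the administered dose will be 75% of the original value".

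**Cetuximab.** After a second hypersensitivity reaction at the slower rate, 5.4.1.2 says "the infusion should be stopped and the subject should be removed from the study". Its next sentence, on severe reactions, stops only the drug: "If a subject experiences a Grade 3 or 4-allergic/hypersensitivity reactions at any time, cetuximab should be discontinued". If cetuximab is withheld too long, 5.4.1.3 says "the subject will be removed from the study treatment". During a chemotherapy delay, 5.4.1.1 keeps cetuximab going: "in the event that the next infusion of chemotherapy is delayed, the subject will receive cetuximab as previously planned". Section 5.4.2 adds that toxicity due to chemotherapy alone does not modify or interrupt cetuximab.

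**General rule (4.2.4).** "The patient must be withdrawn from study treatment in the event of any of the following". A chemotherapy delay is not named in the list that follows.

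**Endpoint and analysis.** The primary endpoint is the 2-year overall survival rate. Patients not known to have died are censored at the last date known alive (8.3.4). The primary efficacy analysis uses the per-protocol set, which retains patients who stopped early for toxicity (8.1).

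**The concern.** There are two problems of different strength.

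The first is a dosing contradiction. A patient whose counts or diarrhoea hold up chemotherapy for more than two weeks is to leave the study under one section and to receive reduced cisplatin under the next.

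The second is the wording. The heading of 4.2.4 itself distinguishes leaving the study from leaving study treatment, so the choice of word carries meaning. If a site took the literal meaning and stopped recording survival status, the patients removed would be those with marked toxicity. They would stay in the primary analysis set but be censored early. If their prognosis were worse than that of the remaining patients, the censoring would be informative and the Kaplan-Meier 2-year survival rate would be too high.

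**Working it through.** **Step 1: do the two delay rules meet in one patient?**

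| Trigger | 5-FU (Table 3) | Cisplatin (5.4.3.1) |
|---|---|---|
| Neutrophils < 1.5 x 10⁹/L | delay | hold |
| Platelets < 100 x 10⁹/L | delay | hold |
| Diarrhoea grade 2-3 | delay | hold |
| After more than two weeks | leaves the study | restart at 75% |

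Section 4.1 schedules both drugs on the same days: 8-11, 36-39, 71-74 and 99-102 in arm A; 1-4, 29-32, 64-67 and 92-95 in arm B. A shared trigger therefore delays both. Reading the 5-FU sentence as a rule for 5-FU alone does not resolve the conflict, because a patient who has left the study cannot receive protocol cisplatin. The conflict is confined to shared triggers. A delay of cisplatin alone is a different case (for raised creatinine, Table 5 restarts at 50%).

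**Step 2: which provisions speak of the study, and which of treatment?** Sections 5.4.2.1 and 5.4.1.2 say study. Sections 4.2.4 and 5.4.1.3 say study treatment. No sentence states whether survival follow-up continues after removal under the first pair.

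**Step 3: how large could the effect on 2-year survival be?** The plan gives no figure for the share of patients removed or for their prognosis, so there is no stated value to reproduce. What follows is an illustration on assumed inputs.

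- Overall true 2-year survival: 0.40 (the plan's baseline level, 8.3.2).
- Share removed: w = 0.05 to 0.15, about 2 to 5 of 33 patients (assumption). 33 per arm is the lowest row of Table 10.
- True 2-year survival of those removed: S_r = 0.20 to 0.30 (assumption).
- Removal time: t0 between day 29 + 14 = 43 (course 2) and day 92 + 14 = 106 (course 4) in arm B. This assumes no removal at course 1 and counts days as if from randomisation.
- Exponential survival in each group, and every removed patient censored at t0 (assumptions).

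Formulas, with k for those not removed:

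- S_k(730) = (0.40 − w·S_r) / (1 − w)
- S_x(t) = S_x(730)^(t/730), for x = r or k
- Kaplan-Meier estimate = [w·S_r(t0) + (1 − w)·S_k(t0)] · S_k(730) / S_k(t0)

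Worked example, w = 0.15, S_r = 0.20, t0 = 43: S_k(730) = (0.40 − 0.03)/0.85 = 0.4353; S_k(43) = 0.9522; S_r(43) = 0.9096. Estimate = (0.15·0.9096 + 0.85·0.9522)·0.4353/0.9522 = 0.4324.

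| t0 | S_r | w = 0.05 | w = 0.10 | w = 0.15 |
|---|---|---|---|---|
| 43 | 0.20 | 0.4097 | 0.4204 | 0.4324 |
| 43 | 0.30 | 0.4049 | 0.4104 | 0.4164 |
| 106 | 0.20 | 0.4085 | 0.4179 | 0.4283 |
| 106 | 0.30 | 0.4044 | 0.4093 | 0.4147 |
| either | 0.40 | 0.4000 | 0.4000 | 0.4000 |

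The arm A days (50 and 113) give the same values to within 0.1 point. The shift is thus +0.4 to +3.2 points. The binomial standard error of a 40% rate at n = 33 is sqrt(0.4·0.6/33) = 0.085, or 8.5 points.

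Between arms, equal removal cancels when the arms do not otherwise differ. With 15% removed in one arm and 5% in the other, the difference shifts by 1.0 to 2.3 points, against a standard error of sqrt(2·0.4·0.6/33) = 0.121, or 12.1 points. The illustration covers the chemotherapy-delay rule only; removal for hypersensitivity, which can occur only in arm A, is not modelled.

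**The case against.** The best defence is that the plan uses the word study loosely and intends follow-up to continue. Section 7.3 requires the end-of-treatment evaluation after premature withdrawal for any reason. Footnote 8 of the schedule starts follow-up three months after that evaluation and makes no exception for early stoppers. Section 8.1 describes patients who discontinued the study for toxicity, yet keeps them in the primary set. Section 8.4 expects only about 5% loss over two years. This defence largely stands: a reader might infer that the plan stops survival follow-up for these patients, and the documents do not support that. What they lack is a sentence saying that it continues. Section 4.2.7, which refers patients to routine guideline care once treatment ends for any cause, does not supply one.

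Three other strong readings also fail.

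- A reader might infer that 5.4.1.2 contradicts 4.2.4 on which reactions end treatment. It does not: 4.2.4 also allows withdrawal for any adverse event where the patient or investigator judges it necessary, so a stricter rule for a recurrent reaction is compatible. Only the choice of word is at issue.
- A reader might infer that cetuximab is left unaddressed, or that 5.4.1.1 contradicts 5.4.2.1. Sections 5.4.1.1 and 5.4.2 do address it, and cetuximab can be given as planned until the two-week limit is reached. What needs aligning is the instruction after that point.
- A reader might subtract the 66 treated patients in 8.4 from the expected 72 to 78 to count those still affected. The populations differ: the Full Analysis Set also requires a post-baseline efficacy measurement.

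It is also fair to object that every input to the bias range beyond the 40% rate, the 33 per arm and the course dates is assumed. That is so, and the range should be read only as an indication of scale.

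**Conclusion.** The dosing conflict is established from the text: for a delay of more than two weeks caused by neutrophils, platelets or diarrhoea, 5.4.2.1 and 5.4.3.1 cannot both be followed. The inconsistency between leaving the study and leaving study treatment is also established.

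The consequence for the primary endpoint is a possibility, not a finding. It requires sites to read the wording literally, to stop recording survival status, and the removed patients to have a different prognosis. If survival status is still collected, or if prognosis does not differ, the bias is zero. Under the assumptions above it is +0.4 to +3.2 points on a 40% rate, at most about 0.38 of one standard error (3.2/8.5). It would act upwards on the experimental arm's rate, which 8.3.4 judges against 40% and 45%, and equal removal in the control arm would not correct that single-arm reading. The point should be settled because the remedy is simple and the endpoint is survival; it does not threaten the trial's validity.

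**What to change.** 1. In 5.4.1.2 and 5.4.2.1, refer to withdrawal from study treatment, in line with 4.2.4.
2. Make the rules for delays over two weeks agree. Either all study treatment ends, and the 75% sentence in 5.4.3.1 is limited to delays of cisplatin alone; or only 5-FU ends, and cisplatin restarts at 75%. The choice is the sponsor's.
3. State what happens to cetuximab after that point, consistently with 5.4.2.
4. In 7.4, state that every randomised patient is followed for survival to the end of study, whichever treatment was stopped, unless consent to follow-up is withdrawn.
5. Ask sites for the survival status of any patient already taken off study under either rule.

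The cost is wording changes in 5.4.1.2, 5.4.2.1 and 5.4.3.1, a sentence in 7.4, and a few extra survival contacts within the existing three-monthly follow-up. With randomisation due to stop by the end of 2016, the dosing correction will reach few patients; the follow-up sentence covers all of them.

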6.1.4 Monitoring of subjects with adverse events

Any AE that occurs in the course of a clinical study must be monitored and followed up until the End of Study Visit. Ongoing adverse events related to study treatment will be followed for 6 weeks (skin toxicities until outcome is known) after end of treatment. In addition SAEs must be reported via a SAE report form (see section 6.1.1.3 Procedure for reporting serious adverse events).

It is the responsibility of the investigator that any necessary additional therapeutic measures and follow-up procedures are performed.

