8.1 Analysis set descriptions

Safety Analysis Set

The safety population includes all patients who received at least one dose of trial medication and for whom at least one post-baseline safety measurement is available.

Full Analysis Set

The Full Analysis Set includes all patients who received at least one dose of trial medication and for whom at least one post-baseline efficacy measurement is available.

Per Protocol Set

This population includes all patients with at least six weeks of trial medication plus all patients who discontinued the study prematurely due to lack of efficacy, death or toxicity. Detailed criteria will be defined before analysis.

All safety analyses will be performed on the Safety Analysis Set. For efficacy analysis of the trial, the primary analyses will be based on the per-protocol set. Additional analyses will be performed on the Full Analysis Set for sensitivity purposes.

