8.3.4 Design and assumptions

- Explorative randomized phase II study with 2 parallel groups.
- Primary endpoint: Overall survival rate after 2 years. Survival time will be calculated from time of randomization until death for any reason, or until last date known to be alive, whichever occurs first. In patients without death, the last date known to be alive will be considered as censored survival time.
- The respective experimental therapy arm would be rated as insufficiently active, if the observed OS rate at 2 years is 40 % or lower, as this corresponds to the standard treatment efficacy.
- On the other hand, the experimental therapy would be considered to be a promising candidate for further development (e.g. in a phase III trial), if the true OS rate at 2 years amounted to 45% or more.

- In order to detect potential differences with respect to the investigated study endpoints between female and male gender, subgroup analyses will be performed for both female and male patients. Furthermore, the potential prognostic impact of gender will be analyzed in a univariate and a multivariate manner. Because an adequate statistical power cannot be expected in each of the two subgroups, the statistical evaluation analyses with respect to gender related differences will be presented in a descriptive manner.

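### Sections 5.4.2.1 and 5.4.1.2 withdraw patients from the study, where 4.2.4 and 5.4.1.3 withdraw comparable patients from study treatment only, and no text secures their survival follow-up

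*Combined protocol and SAP*

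**What the plan says.** Four sections of the combined protocol and SAP deal with stopping for toxicity or delay, and they use two different consequences.

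- Section 5.4.2.1 (5-FU): "If therapy is delayed for longer than 2 weeks, the patient will be withdrawn from the study". I read therapy here as 5-FU, the subject of that section.
- Section 5.4.1.2 (second hypersensitivity reaction at the reduced infusion rate, no minimum grade): "the infusion should be stopped and the subject should be removed from the study".
- Section 4.2.4 (general rule): "The patient must be withdrawn from study treatment in the event of any of the following". Its list includes a cetuximab delay of more than two weeks and hypersensitivity of grade 3 or higher. It does not include a 5-FU delay.
- Section 5.4.1.3 (prolonged cetuximab interruption): "If therapy must be withheld for a longer period of time, the subject will be removed from the study treatment".

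For comparison, section 5.4.3.1 answers a cisplatin delay of more than two weeks with a reduction to 75% of the dose.

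Two rules carry this into the primary analysis. Section 8.3.4 sets the censoring of overall survival: "In patients without death, the last date known to be alive will be considered as censored survival time". Section 8.1 bases the primary efficacy analysis on the per-protocol set, which retains "all patients who discontinued the study prematurely due to lack of efficacy, death or toxicity".

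**The concern.** The section 4.2.4 heading names both the study and study treatment, so the protocol has words for the two concepts. A site that takes sections 5.4.2.1 and 5.4.1.2 at their word could close the patient's file, and the last date known alive would then be near the withdrawal date. The patient would stay in the primary analysis set with a survival time of a few months for a 24-month endpoint. The reason for censoring would be toxicity, which may be related to survival, so the Kaplan-Meier assumption of unrelated censoring would be in doubt. The hypersensitivity rule would add such losses in the cetuximab arm only.

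The 5-FU rule can plausibly be reached. Table 3 has a row for "Further non-hematological toxicities (except nausea/vomiting and alopecia") that holds 5-FU at grade 2-3 until grade 0-1, while Table 7 continues radiotherapy at grade 2 dysphagia. Section 5.5.1 expects acute reactions to settle two to four weeks after radiotherapy ends.

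**Working it through.** **1. The plan's own loss assumption.** Section 8.4 assumes about 5% lost to follow-up over two years in Table 10. Take the row with 2 x 36 patients and 35% control survival. HR = ln(0.6702)/ln(0.35) = 0.3812, as stated. By the Schoenfeld formula (two-sided 5%, 80% power), events = 4(1.960 + 0.842)²/(ln 0.3812)² = 33.8, so 34 against the stated 35. Expected events under exponential survival with 5% loss are 34.5. The table reproduces to within one event. Five per cent is 0.05 x 33 = 1.65 to 0.05 x 36 = 1.8 patients per arm.

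**2. Can a delay exceed two weeks?** Radiotherapy starts on the first chemotherapy day (section 5.5.1), at five fractions a week. Course 2 therefore falls on radiotherapy day 29 in both arms (Arm A: study day 36 - 7). Fraction 33 falls on 7 x floor(32/5) + (32 mod 5) + 1 = day 45. Grade 2 dysphagia from course 2 to the last fraction would delay 5-FU by 45 - 29 = 16 days, more than 14. It may improve sooner, and the documents give no rate.

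**3. Earliest time at which the two-week limit is reached.** (Planned 5-FU day + 14)/30.44 months, with days from section 4.1:

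| Course | Arm B | Arm A |
|---|---|---|
| 2 | 29 + 14 = day 43, 1.41 months | 36 + 14 = day 50, 1.64 months |
| 3 | 64 + 14 = day 78, 2.56 months | 71 + 14 = day 85, 2.79 months |
| 4 | 92 + 14 = day 106, 3.48 months | 99 + 14 = day 113, 3.71 months |

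The range is about 1.4 to 3.7 months from treatment day 1. Survival runs from randomisation, and that gap is not given. An Arm A delay at course 1 (day 8 + 14 = day 22, 0.7 months) or a second hypersensitivity reaction could come earlier. If the last contact is the end of the six-week follow-up of related adverse events in section 6.1.4, add 42 days: day 85 to day 155, or 2.8 to 5.1 months.

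**4. Shift in the 2-year estimate.** Assume true 2-year survival of 0.40 and exponential survival. With k patients of n censored alive at c months, Sc = 0.40^(c/24), and the Kaplan-Meier value at 24 months is:

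- all k would have died: Sc x 0.40n/(n x Sc - k)
- all k would have survived: Sc x (0.40n - k)/(n x Sc - k)

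For n = 33, k = 1, c = 1.41: Sc = 0.9476, and 0.9476 x 12.2/30.27 = 0.382, a shift of -1.8 points. For n = 33, k = 1, c = 3.71: Sc = 0.8679, and 0.8679 x 13.2/27.64 = 0.414, a shift of +1.4 points. With n = 36 both shifts are smaller (-1.65 and +1.3). At c = 5.1 months and n = 33 the upper value is +1.5. For k = 2 the range is -3.7 to +3.0 points. If the censored patients have the same prognosis as the rest, the expected shift is 0.

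**5. Scale.** The standard error of a 40% rate is √(0.40 x 0.60/33) = 8.5 points, or 8.2 points for n = 36.

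**6. Power, for illustration.** If an assumed 5% or 10% of patients were censored this early and contributed no events, expected events in the row above fall from 34.5 to 32.8 or 31.1, and power is about 79% or 77%.

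**The case against.** The strongest reply is that the protocol can be read as following these patients anyway. Sections 4.1 and 7.3 require the end-of-treatment evaluation at premature withdrawal for any reason. Footnote 8 of the assessment schedule starts follow-up three months after that evaluation and does not limit it to patients who complete treatment. Section 4.2.7 has patients followed by national guideline after treatment ends for any cause. The wording also looks loose. In section 5.4.1.2 a grade 3-4 reaction leads only to withdrawal from treatment, while a possibly milder second reaction leads to removal from the study, which makes little sense if taken literally. This weakens the concern, but none of these texts says that follow-up for survival continues once a patient is withdrawn from the study, so the conflict remains.

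A reader might infer that the two sentences themselves censor survival at withdrawal. They do not. Section 8.3.4 censors at the last date known alive, and nothing forbids recording a later date for a patient who has not withdrawn consent. The months above are therefore earliest values. The six-week window is not a firm limit either. Section 6.1.4 says "Ongoing adverse events related to study treatment will be followed for 6 weeks (skin toxicities until outcome is known) after end of treatment", but the sentence before it follows every adverse event to the end-of-study visit, and section 4.2.4 keeps medically withdrawn patients under supervision until the events resolve or return to baseline.

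A reader might also treat the 5% loss figure as a limit that a second patient breaches (2/36 = 5.6%, 2/33 = 6.1%), or compare the shift with the 5 points between 40% and 45% as if that gap alone decided the trial. The 5% is an approximate input to Table 10. Section 8.4 rests the conclusion on the survival rate with its confidence interval, the reference arm and toxicity.

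**Conclusion.** The inconsistency holds. Two toxicity-related rules withdraw patients from the study where parallel rules withdraw them from study treatment, and no text secures their survival follow-up. Whether this harms the primary endpoint depends on sites acting on the literal wording, and the documents give no frequency for either event. A claim that the trial loses these patients, or that its 2-year estimate is biased, is not supported.

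The shift of -1.8 to +1.4 points per affected patient is a best-case and worst-case bound. It rests on 33 to 36 patients per arm, 40% 2-year survival, exponential survival, and censoring at the earliest times for courses 2 to 4. It is small beside the standard error. It also assumes that the patient counts as a toxicity discontinuation or already has the six weeks of medication that section 8.1 requires. Section 8.1 leaves its detailed criteria to be defined before analysis.

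Severity is minor to moderate: a wording fault with a conditional effect on the primary endpoint and a cheap remedy.

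**What to change.** - In section 5.4.2.1, change the consequence of a delay of more than two weeks to: *withdrawn from study treatment; follow-up for survival continues per 7.4*.
- In section 5.4.1.2, change the consequence of a second reaction to: *removed from study treatment; follow-up for survival continues per 7.4*.
- For patients already withdrawn under either sentence who have not withdrawn consent, obtain vital status at 24 months from randomisation. This is the larger part of the benefit, because section 8.4 reports 66 patients already randomised and treated, of 72 to 78 expected in the full analysis set.

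The cost is an amendment to two sentences. Each affected patient needs one vital-status query at month 24, or at most seven three-monthly contacts (months 6, 9, 12, 15, 18, 21 and 24). Treatment rules, safety limits, sample size and Table 10 do not change. If therapy in section 5.4.2.1 was meant more broadly than 5-FU, the new wording does no harm.
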